## LIST OF ABBREVIATIONS AND ACRONYMS

AE	Adverse Event
CDC	Centers for Disease Control and Prevention
CDMS	Clinical Data Management System
CFR	U.S. Code of Federal Regulations
CITI	Collaborative Institutional Training Initiative
CLIA	Clinical Laboratory Improvement Amendments
DBS	Dried Blood Spots
DSMB	Data Safety Monitoring Board
eCRF	Electronic Case Report Form
FDA	U.S. Food and Drug Administration
GCP	Good Clinical Practice
GLMM	Generalized Linear Mixed Model
GSN	Geosocial network
HBsAg	Hepatitis B surface antigen
HIPAA	Health Insurance Portability and Accountability Act
HIV	Human Immunodeficiency Virus
ICF	Informed Consent Form
ICH	International Conference on Harmonization
IRB	Institutional Review Board
ISO	International Organization for Standardization
LGBT	Lesbian, Gay, Bisexual, and Transgender
MMS	Mobile messaging service
MSA	Metropolitan Statistical Area
MSM	Men who have sex with men
NIH	National Institutes of Health
OHRP	Office for Human Research Protections
PCR	Polymerase chain reaction
PEP	Post Exposure Prophylaxis

PrEP	Pre-Exposure Prophylaxis
RPR	Rapid plasma reagin
SMS	Standard messaging service
STI	Sexually Transmitted Infection
TAF/FTC	Tenofovir alafenamide/emtricitabine
TDF/FTC	Tenofovir disoproxil fumarate/emtricitabine
TFV-DP	Tenofovir diphosphate
YBMSM	Young Black Men who have sex with men
FTC-TP	Emtricitabine triphosphate

## 1. INTRODUCTION

### Background and Rationale

Pre-exposure prophylaxis (PrEP) has demonstrated high effectiveness and efficacy for HIV prevention for men who have sex with men (MSM), who are disproportionately impacted by HIV. The US Centers for Disease Control and Prevention (CDC) estimates that approximately 1.2 million US adults are eligible for PrEP, including 492,000 MSM. PrEP prescriptions are growing exponentially, with over 79,000 prescriptions between 2012 and 2015 in the US, yet the benefits of PrEP protection are accruing inversely to HIV acquisition risk, with young and minority MSM less likely to access PrEP despite higher risk.

Studies indicate expanding PrEP access would be both cost-effective and feasible for MSM, including MSM of color. Modeling indicates that if PrEP were scaled to cover 40% of behaviorally eligible MSM in the United States, approximately 25% of new HIV infections among all MSM would be averted over the next ten years.

Scale-up of PrEP may be limited by the burden to the healthcare system. Guidance issued by CDC and by WHO calls for quarterly follow-up visits for those on PrEP, to include behavioral and laboratory assessments and intervention as needed. The burden of quarterly visits for MSM, if PrEP was brought to scale at an 80% level among those eligible, would be 1,576,000 annual patient visits. We estimate such visits would entail over 3 million hours of patient time, with an opportunity cost of \$68 million annually, in addition to the millions spent on clinician time and clinic facilities.

In 2015, MSM continue to account for two-thirds of new HIV cases in the United States. Within this elevated risk group, Black MSM (10,315/26,645, 39%) and young MSM aged 20-34 (15,381/26,645, 58%) bear disproportionate burdens, and represent appropriate populations for intervention. As PrEP is being brought to scale, it has been shown to have high effectiveness: in international settings the PROUD study found 86% reduction in anticipated infections, and the IPERGAY study's open-label extension found 95% reduction. In domestic settings, an observational assessment of Bay Area Kaiser HMO patients found no new cases of HIV among their PrEP users, despite common bacterial STI, with 855 person years of follow-up.

Implementation data from Washington D.C., San Francisco, and Miami have found that at 12months post-PrEP initiation, persistence in PrEP care was 79%, and similarly found PrEP adherence among those maintained in care at 80%. Given low adherence among US MSM in the iPrEX RCT (56%), higher levels of adherence can likely be attributed to patient awareness of using an active medication with documented efficacy, as opposed to the blinded RCT participants not knowing if the medication was protective, or whether they were receiving a placebo that couldn't work. Interventions that promote improved persistence in PrEP care are an essential part of optimizing the impact of PrEP.

Our theoretical model regarding a PrEP care continuum, as retrospectively applied to a cohort of young, Black MSM (YBMSM), indicates that a key to achieving high PrEP efficacy will be persistence in PrEP care, yet persistence has been suboptimal in studies among YBMSM. In a cohort study of YBMSM with PrEP offered as standard of care, 38/110 participants accepted, but within 6 months of initiation 16% (n=6) ceased PrEP. Of three observed seroconversions, two were among those who had started but subsequently ceased PrEP. In ATN 113, 60% of participants had protective PrEP dosing at 4 weeks follow-up, but only 23% maintained at 36 weeks follow-up. Minimizing the participant burden of PrEP while supporting persistence in care could reduce PrEP cascade drop-off.

Young persons in urban areas, and Black persons in urban areas, have lower access to transportation by car, and are therefore more likely to rely on transit methods requiring larger amounts of time. This is important because urban transportation has been identified as a potential barrier to PrEP access.

As effectiveness of PrEP is already established, PrEP@Home could be beneficial to bringing PrEP to scale in a variety of care settings. For large PrEP clinics, home care would enhance capacity for PrEP scale-up given limited space and personnel resources. For instance, Magnet@Strut Clinic in San Francisco has initiated over 1,900 patients on PrEP (close to 2% of total PrEP prescriptions in the United States), and Callen-Lorde in New York has initiated PrEP for over 2,000 PrEP. In the past, Magnet has at times been limited in accepting new PrEP patients, attributing this problem to lack of available provider time and clinic space, the bulk of which was occupied by PrEP visits. Similarly, other common venues of PrEP provision have limited “brick and mortar” space to add substantial numbers of new patient visits, an issue that home care could address.

Electronic communication, such as that used by PrEP@Home surveys and patient portal, is now the predominant mode of communication for young people. Male adolescents send or receive over 2800 mobile messages (MMS and SMS) a month on average, 96% of MSM teens use Facebook, and the predominant final activity immediately prior to sleep for 69% of adolescents involves electronic media. Simply put, mobile and electronic interactions are now the dominant means of communication and interaction for young men. Moreover, 75% of young MSM use geosocial network (GSN) websites, and 60% use GSN apps, with a majority reporting frequent use and reporting an intended use for “meet(ing) guys for sex.” Smartphone ownership is particularly high among YBMSM, with ownership higher in groups identifying as Black (70%) or under age 30 (85%) than ownership in the general US (63%). Moreover, smartphone ownership is increasing as sub-\$100 smartphones proliferate.

Relative to clinic-based STI tests, mail-in tests have been shown to improve rescreening rates, cost-effectiveness, and acceptability. Home-based, self-collected test kits for chlamydia increased rescreening rates by over 20% in one study. Another study found home-based testing for chlamydia and gonorrhea to be more cost-effective than clinic-based testing. Moreover, a majority of MSM prefer home-based HIV/STI tests to clinic-based tests, with 75% willing to undergo routine home screenings with no monetary incentive.

A home-based PrEP support system could address some patient concerns regarding PrEP uptake. One limitation of PrEP is the heavy burden of follow-up visits borne by patients, including indirect cost (i.e. absence from paid work, need for child-care) and direct cost (i.e. transport, copayments) that could lead to problems with PrEP adherence. The home care system for PrEP is comprised of inexpensive, commonly available laboratory supplies such as finger prick devices, swabs, and microtubes. Patient self-completion surveys that simulate clinician visit typical questions may allow for clinicians to have a higher volume of patients due to time savings. Given these inputs, the home care system has the potential to be cost saving, depending in part on the level of human resources required to maintain patients in home care.

A home-based monitoring approach could facilitate PrEP prescription by non-HIV specialist doctors. Expanding access to PrEP will involve providing services to HIV-negative MSM who frequently do not visit HIV specialist providers. Provider type and current care models may pose limitations to PrEP scale-up. A survey of providers found that generalist physicians, relative to HIV specialists, were more likely to rate time required for counseling (19% and 6%, respectively) and time for clinical monitoring (23% and 10%) as barriers to providing PrEP. A qualitative study found that providers believe their current care models are poorly suited to PrEP, particularly

surrounding extensive follow-up and monitoring required. In a pilot test that replaced a regular clinician visit with a PrEP@Home visit, 55/58 participants successfully renewed their PrEP prescriptions without an in-person provider visit. Forty percent (22/55) indicated they would have a greater likelihood of remaining on PrEP if the home care system was made available and 87% (48/55) indicated they would like to use PrEP@Home again.

A home-based PrEP monitoring and support system could decrease provider and patient burden, increase patient willingness to initiate or remain on PrEP, facilitate the provision of PrEP by primary care practitioners who are less experienced in counseling to prescribe PrEP, and might be cost-saving. This study will be the first to assess the feasibility of home-based PrEP support among providers.

**The purpose of this study is to assess the maintenance in PrEP care, not to study the effectiveness of PrEP medication. Adherence to follow-up visits will be assessed through several methods. PrEP will be prescribed according to standard of care practices.**

### 3. STUDY OVERVIEW

#### 3.1 Study Design

The study is a stratified randomized, controlled trial comparing PrEP@Home intervention care to standard of care control (i.e. patients being seen quarterly in clinic with a provider), with primary outcome of having protective levels of TFV-DP (700 fmol/ml or greater) and secondary outcome of retention in PrEP care, as measured by photo of dated prescription label.

[figure not shown]
A screening will be conducted online and involve a screening consent and questions to determine initial eligibility. This will be followed by a full consent (if eligible), a baseline survey, and the return of self-collected specimens for testing to determine clinical PrEP eligibility. Those eligible for the study will be enrolled into the trial and randomized to either intervention (PrEP@Home) or control (standard of care). Participants assigned to the PrEP@Home intervention will have a baseline teleconsultation with a site study clinician who will be responsible for prescribing PrEP as indicated. Intervention participants enrolled prior to May 2022 will be offered telemedicine consultations at 1, 3, 6, 9 and 12 months, and will complete quarterly home specimen collection for laboratory tests recommended by CDC at each time period. Individuals enrolled after May 2022 will be offered telemedicine consultations at 1, 3, and 6 months, and will complete quarterly home specimen collection for laboratory tests recommended by CDC at each time period. The study virtual visits consist of surveys, specimen collection, and telemedicine consultation. Those assigned to the control condition will be referred to a publicly available website that geolocates the nearest PrEP provider, [www.PrEPLocator.org](http://www.PrEPLocator.org). Both conditions will have identical TFV-DP kit collection for primary outcome assessments at month 6 (and 12 months for those enrolled before May 2022) and app-based surveys for secondary outcomes assessments at baseline, 3, 6, (and 9 and 12 months for those enrolled before May 2022).

Study sites in Atlanta, GA, Boston, MA, Jackson, MS, St. Louis, MO, and Cleveland, OH, will allow for recruitment to focus on MSM known to be at highest risk of acquisition and with documented lower levels of persistence in PrEP care. The sample of 396 will be composed of at least 50% Black and 50% younger (aged 18-34) participants, including at least 25% YBMSM.

[figure not shown]
Prior to the RCT starting, a small pilot with 5-10 participants will be conducted to test and verify logistics of lab processing procedures. Included in the pilot will be shipping lab specimens, tracking the specimen samples through processing and testing the app systems shipping and lab results components.

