Stage 3 screening will be verification that HIV 4th generation and creatinine clearance tests indicate eligibility and a PrEP prescription has been filled. Using our electronic software (described below) the survey will prompt participants to use their smartphone to take a photo of their prescription label that identifies their name, date of prescription, and the medication name. We anticipate this to occur within one week of receiving the prescription. Once this brief process is completed, participants will be enrolled into the trial.

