#### Authorization for Release of Information:

All participants, in both intervention and control arms, will be contacted during the study period to fill out an optional Authorization for Release of Information form. This form will provide study staff with permission to contact each participant's pharmacy where they fill their current PrEP prescription. Participants will be asked to sign the form and provide contact information for their pharmacy (i.e. pharmacy name and number, address, and/or phone number). Study staff and clinicians will contact pharmacies to collect information on prescription fill dates and quantities. This information will be used to better understand study outcomes, particularly the primary adherence outcome for participants who have not returned their DBS cards.

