#### **6.4 Referrals**

*During Study:* Treatment referrals will be provided to participants for positive STI laboratory results. Staff will work with local resources to facilitate access to care at free or low cost. In the case of a positive HIV test, participants will cease PrEP dosing, be discontinued from the study, and be linked to care the next business day. For positive STI tests, participants will have PrEP prescriptions initiated or renewed, and be referred to STI treatment at a local agency. Site study staff will follow-up with participants testing positive for STI to ensure they have sought appropriate care. In cases of participant-opted discontinuation of PrEP, the participant's rationale for discontinuing PrEP will be documented.

*End of Study:* Participants in the intervention arm will be linked to PrEP care by study staff. Control arm participants will continue with their regular care.

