### **9.2.1 Adjusted analyses**

GLMM models will control for potential confounding for factors such as medication self-efficacy and motivation to take PrEP. (1) Adjusted analyses will be conducted to control for changes in PrEP eligibility over time for participants in each trial arm, per CDC guidelines, using an additional interaction term between eligibility and treatment arm. (2) Per protocol assessments will be conducted that account for potential changes in intervention as delivered; for instance, this would account for participants assigned to the intervention condition opting to instead receive standard of care PrEP from their local clinician.

A number of secondary analyses will be conducted using GLMM models. (3) Intervention impact on the secondary outcome of PrEP prescription persistence will be determined using analogous logistic regression models. (4) Secondary analysis will be conducted to model  $\log_{10}$  (TFV-DP levels), using a linear mixed model. Other specific and aggregate measures of safety include: renal function, HIV incidence, and incident bacterial STI across study arms.

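### Retention in PrEP care is measured only by a prescription-label photo, with no follow-up window or missing-photo rule, so failing to upload and stopping PrEP are confounded

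*Combined protocol and SAP*

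**What the plan says.** Section 3.1 names one secondary outcome, the "secondary outcome of retention in PrEP care, as measured by photo of dated prescription label". Section 9.2.1, item (3), gives its analysis: "Intervention impact on the secondary outcome of PrEP prescription persistence will be determined using analogous logistic regression models".

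The photo step itself is described only at enrolment. In Stage 3 of Section 3.5.2 the survey asks participants to "take a photo of their prescription label that identifies their name, date of prescription, and the medication name", and Section 6.2 repeats the request after the first prescription, which covers three months. The procedures schedule in the appendix has no row for a photo, and Section 10.4 attaches no payment to one.

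Other information on stopping is collected:

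- Section 3.1 plans, in both arms, "app-based surveys for secondary outcomes assessments at baseline, 3, 6" months, and at 9 and 12 months for earlier enrollees. Section 6.5.1 says surveys ask about adherence.
- Section 6.3 asks participants in both arms to "fill out an optional Authorization for Release of Information form". With that release, "Study staff and clinicians will contact pharmacies to collect information on prescription fill dates and quantities". The stated purpose is to understand study outcomes, "particularly the primary adherence outcome for participants who have not returned their DBS cards".
- Section 6.4 says: "In cases of participant-opted discontinuation of PrEP, the participant's rationale for discontinuing PrEP will be documented".
- Section 7.4 anticipates that some participants will report having stopped, but uses this only when considering incentives for returning cards.

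None of these sources is written into the definition or the analysis of the secondary outcome.

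**The concern.** A label photo can show directly that a prescription was filled. Its absence has two explanations: the participant stopped, or the participant continued and did not send it. Every randomised participant has already supplied one label photo, because this is a condition of randomisation (Section 5.2). Only evidence dated during follow-up can therefore separate retained from not retained, and the plan does not say which dates count.

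Without a coding rule the analyst must choose one after the data are in. If no photo means not retained, willingness to upload becomes part of the outcome. If participants without a photo are left out, the analysed records are mostly successes.

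Contact with the study differs by arm, so equal upload cannot be taken for granted. Section 6.1.2 specifies electronic reminders for intervention participants. Section 5.1 gives them the full app and controls only portions of it. Under Section 4, study clinicians can renew intervention-arm prescriptions, while controls are followed by outside providers.

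The outcome matters beyond its own test. It is named in Aim 2.1, persistence estimates from Aims 1 to 2.1 feed the transmission model (Section 9.4) and through it the cost-effectiveness analysis (Section 9.6), and the DSMB monitors persistence (Section 8.1).

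**Working it through.** **Inputs from the documents.** Arm sizes 264 and 132 (Section 5.2). Two-sided 5% level (Section 9.2) and pooled two-proportion z-test (Section 9.1), both stated for the primary outcome. Persistence of 79% at 12 months, from demonstration projects cited in Section 1.

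**Assumptions.** Upload rates among persisters, and true persistence values other than 79%. The documents give neither for this trial. The z-test at a single visit stands in for the planned logistic model and is used only to gauge size.

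**The plan's own figure.** No power is stated for the secondary outcome. The primary-outcome statement reproduces: 396 × 0.9 = 356.4 evaluable (237.6 and 118.8), 0.658 versus 0.50, pooled z-test, power 0.82 against the stated 80%. This neither supports nor weakens the point; it serves only as a base for step 3.

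**1. False difference when no photo is coded as not retained.** Let true persistence be *p* in both arms and upload among persisters *u*I (intervention) and *u*C (control). The apparent difference is *p* × (*u*I − *u*C).

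- 0.79 × (0.95 − 0.80) = 0.1185, or 11.9 points
- 0.79 × (0.90 − 0.85) = 0.0395, or 4.0 points

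The first case shows the rejection rate. The observed proportions are 0.79 × 0.95 = 0.7505 and 0.79 × 0.80 = 0.632; the pooled proportion is 0.711, the null standard error 0.0483 and the unpooled standard error 0.0497. Then 1 − Φ((1.96 × 0.0483 − 0.1185)/0.0497) = 0.68, against a nominal 0.05.

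| True persistence, both arms | Upload 95% v 80%: points (rejection rate) | 90% v 80% | 90% v 85% |
|---|---|---|---|
| 50% | 7.5 (0.29) | 5.0 (0.16) | 2.5 (0.08) |
| 70% | 10.5 (0.53) | 7.0 (0.27) | 3.5 (0.105) |
| 79% | 11.9 (0.68) | 7.9 (0.36) | 4.0 (0.13) |

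If the rates are reversed, so does the sign: at 79%, upload of 80% in the intervention arm and 95% in control gives −11.9 points.

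**2. Participants without a photo left out.** If a photo is the only evidence, those analysed are nearly all retained in both arms, whatever the truth, and there is little to compare.

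**3. Equal but incomplete upload.** There is no false difference, but a true one shrinks. Borrowing the primary outcome's 0.50 versus 0.658 with 10% loss, upload of 90%, 80% or 70% in both arms reduces 15.8 points to 14.2, 12.6 or 11.1, and power from 0.82 to 0.72, 0.62 or 0.51.

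**4. What pharmacy records would recover.** If a fraction *c* of non-uploading persisters in each arm has a pharmacy record, the false difference is multiplied by (1 − *c*). The 11.85 points become 8.9, 5.9, 3.0 and 0 at 25%, 50%, 75% and 100%. If coverage differs by arm, the gain can be small: 75% in the intervention arm and 25% in control leaves 0.79 × [(0.95 + 0.05 × 0.75) − (0.80 + 0.20 × 0.25)] = 0.79 × (0.9875 − 0.85) = 0.109, or 10.9 points.

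**The case against.** The plan is not blind to stopping. Surveys are scheduled in both arms for secondary outcomes, reasons for stopping are documented, and pharmacy fill data are sought from everyone. The enrolment photo is prompted by a survey; if follow-up works the same way, which is an inference, a completed survey without a current label is an observation and not a gap. The label carries a date, so an old label can itself point to a lapse. A reader might infer that the outcome records only successes, or that stopping can never be told from not uploading. The documents do not support either: the first needs a rule that drops missing photos, which the plan does not state, and the second ignores these other sources.

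A reader might also infer a bias in favour of the intervention. The documents do not establish that. Kit tracking and app surveys are in both arms (Sections 4 and 5.1), Section 3.7 describes app reminders for participants generally, telemedicine runs on Zoom and not in the app (Section 10.5), and survey payments are equal (Section 10.4). No upload rate is given for either arm.

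Finally, this is a secondary outcome. The primary drug-level comparison does not use follow-up photos, and Aim 1 itself treats drug levels as an indication of maintenance in care. The schema figures and some appendix pages are not available here, so a photo schedule may exist there.

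These points limit the claim but do not answer it. The definition names the photo alone, no other source is attached to it, and the pharmacy release is optional and aimed mainly at the primary outcome.

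**Conclusion.** The point holds for the outcome as defined: non-upload and stopping are confounded, because the measure is the photo alone and the visible text gives neither a date window nor a missing-photo rule. Under the coding in which no photo means not retained, the illustrative false difference at 79% true persistence is 4.0 to 11.9 points, with a rejection rate of 0.13 to 0.68 in place of 0.05. These sizes rest wholly on assumed upload rates and show sensitivity, not an expected bias; equal upload gives no false difference. Direction is unknown. The primary outcome is unaffected. The definition should be settled before this outcome is analysed and before persistence estimates are passed to the modelling.

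**What to change.** Amend the SAP as follows, identically for both arms:

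- **Definition.** At each follow-up visit, a participant is persistent if a label photo or a pharmacy record shows a fill covering a stated window around that visit.
- **Denominator.** All randomised participants.
- **Observed failures.** Use self-reported or documented stopping to identify them, and state which source prevails when sources conflict.
- **No evidence either way.** Score as not persistent in the main analysis.
- **Sensitivity analyses.** One treats participants with no evidence as missing; one is restricted to participants with a pharmacy release.
- **Reporting.** Give upload and release rates by arm, so that readers can judge how far steps 1 and 4 of the working apply.

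The cost is SAP wording plus use of pharmacy data already sought in both arms. The downside is that the release is optional. Some non-uploading persisters will still be scored as not persistent, and this could differ by arm; the main analysis keeps that weakness in reduced form, which is why the sensitivity analyses and arm-specific rates are needed.
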